Early Mobilization of Older Adults in the Cardiovascular Intensive Care Unit

I. RESEARCH QUESTION

Is an early progressive mobilization program safe, feasible, and effective in older adults in the Cardiovascular Intensive Care Unit (CICU)?

II. HYPOTHESES

1. An early mobilization (EM) program is safe, feasible, and effective in older adults in a Canadian tertiary care academic CICU.
2. Level of function on CICU discharge and time spent lying in bed during hospitalization is associated with health-related quality of life scores and functional status at longer-term follow-up.

III. SPECIFIC AIMS

Aim #1: To determine functional status and longer-term patient-centered outcomes of older adults admitted to the CICU prior to the implementation of the EM program (“pre-intervention” cohort)

Aim #2: To assess the safety and feasibility of an EM program in a Canadian academic tertiary care CICU

Aim #3: To determine the effectiveness of EM at improving the functional status of older adults during CICU admission and improving longer term patient-centered outcomes (“intervention” cohort)

Aim #4: To evaluate the association of daily time spent lying in bed with functional status at CICU discharge and following hospital discharge

Aim #5: To assess the amount of skeletal muscle mass loss during admission for acute cardiovascular disease

IV. BACKGROUND

A. Physical Function and Impairment in Older Adults in the Critical Care Unit

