Prior to the implementation of the EM intervention, nurses will ascertain and record the prehospital LOF, admission LOF, and LOF on the day of CICU transfer (Appendix A), but will continue usual mobilization practices. Patients who meet eligibility criteria for the EM intervention will be prospectively enrolled over a 3-month period (“pre-intervention cohort”) by a member of the research team during CICU admission. Informed consent will be obtained by a member of the research team. Following discharge, a member of the research team will review the medical record to extract demographic data (age, sex), comorbid illnesses, primary admission diagnosis, frailty status, adverse events during mobilization (falls, dislodgements, and injuries), mobilization activities, length of critical care unit stay, length of hospital stay, mortality, and discharge location.

Intervention

On admission to the CICU, the patient’s treating nurse will assess the patient for the EM program. Patients participating in the EM program will be assessed for enrolment in our study by a member of the research team and will obtain informed consent during CICU admission (“intervention cohort”). The potential participants are likely to be competent and medically fit to be approached for informed consent as patients who are not medically fit will be excluded from the early mobilization program based on clinical factors, which include hemodynamic criteria.

The EM program consists of a progression of functional activities from LOF 0 (lowest mobility) to 5 (highest mobility). Each LOF has 3 primary activities designed to promote the patient to the next level. The nurse will begin with mobility activities based on the LOF that matches the patient’s current status. The nurse and clinical partner will attempt and/or complete each LOF activity once per shift. Physiotherapy assistance is available if required, although not obligatory. Nurses will also provide documentation and education to patients and families on

how to perform and assist with certain activities. LOF, activity attempts/completion, and adverse safety events will be recorded on an EM flowsheet. The intervention will start while the patient is in the CICU and will continue until discharge from the CICU.

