To introduce the EM protocol to the nursing staff, the nurse and physician champion will provide a series of in-service training sessions. Physicians routinely caring for older adults in the CICU and rotating trainees will receive education in the CICU through “Lunch and Learn” conferences. Weekly audits will be performed by the nurse champion to assess for adherence to the EM protocol. Reminders and further education will be provided if necessary. Monthly status reports will be created and disseminated to the nurses and the CICU team.

Frailty will be assessed on admission using the Clinical Frailty Scale (CFS) by the patient’s nurse or a member of the research team (Appendix B).³² The CFS is a simple bedside assessment tool that uses a single global judgement-based measure to assign a score from 1 (very fit) to 9 (terminally ill) with increasing scores from 5 to 8 indicating more advanced frailty.²⁰ The CFS correlates with more comprehensive frailty tools, has been shown to accurately diagnose frailty in critically ill and acute cardiac populations, and provides short and long-term prognostic information.^{20, 21, 33}

Enrolled participants will be approached to participate in this prospective substudy. Patients accepting participation will be asked to wear an accelerometer monitor during CICU stay until the end of hospitalization to capture the time spent in each mobility position. Body composition parameters including skeletal muscle mass and fat mass will be measured daily with a segmental multi-frequency bioimpedance scale.

Instruments

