In the patients wearing the accelerometer, data will be recorded on the total time spent in each mobility position, the daily average time spent in each mobility position, the average duration of time for each bout of sitting, standing, and walking, and sleep duration. The step count will also be recorded. The change in skeletal muscle mass from CICU admission to hospital discharge will be recorded.

We will determine which covariates predict improvement in LOF (“responsiveness”) and which ones do not (“non-responsiveness”). We will assess the recovery of physical function at 1 month and 12 months as measured by the SF-36 physical component summary score. We will compare the SF-36 scores of the highest scoring tertile of LOF on hospital discharge with the lowest scoring tertile. We will also compare hospital readmission at 30 days and discharge home vs. healthcare facility.

For safety, we will record the composite and individual components of the number of falls, injuries, and dislodgements over the total number of attempted mobility activities. The results from the intervention cohort will be compared to the pre-intervention cohort for all results.

Data Collection Procedures

Following discharge, a member of the research team will capture the following hospitalization data from the electronic medical record (Chartmaxx, Quest Diagnostics, Madison, New Jersey) for each subject: age, sex, primary admission diagnosis, comorbidities, level of function assessments, CFS score, length of CICU stay, length of hospital stay, discharge location, and referral to cardiac rehabilitation.

Availability of Participants

In the fiscal year 2016-2017, there were 1,356 admissions to the JGH CICU (mean age 68 years old; 477 female (35%)). There were 1,034 patients (76.3%) age ≥ 60 years old. The mean CICU length of stay was 3.3 days and the mean hospital length of stay was 9.5 days. Only one in five patient stays was less than 24 hours in length.

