From the pilot data, we conservatively estimate that about one-third of patients will not be eligible for the study and about 70% will agree to participate. We estimate that the loss of patients to 12 month follow-up will be approximately 10% as the vast majority of CICU patients are followed by hospital-affiliated cardiologists prior to admission or are assigned to one following CICU discharge. Given these estimates, approximately 75 patients are expected to be enrolled and followed during the pre-intervention period and 300 patients are expected to be enrolled and followed during the 12 month intervention period.

Data Analysis

Since the response variable, LOF mobility, is an ordinal variable measured at different timepoints, a cumulative logit model for repeated measurements will be fitted using generalized estimating equations. The model permits us to take into consideration the structure of the correlation between the observations. The model will then be adjusted using covariates of interest, such as age, sex, EM adherence, time spent lying in bed, and illness severity score. Predictors of change in LOF during CICU stay and following hospitalization will be assessed using linear regression. Predictors of EM adherence will also be evaluated using linear regression. All statistical analyses will be performed using SAS version 9.4 by [name], a senior biostatistician affiliated with the Lady Davis Institute Center for Epidemiology.

VII. RESOURCE AVAILABILITY AND SUPPORT

The CICU at the JGH has 16 beds equipped for advanced hemodynamic support and 32 ward beds with telemetry available. Patients are admitted to the CICU mainly for acute primary cardiovascular disease.

The nurse champion's role is to attend EM team meetings, provide education to nursing and clinical partners, and ensure nursing adherence to the protocol. A review of the CICU environment conducted with physiotherapists from the EM team has ensured that the CICU is already equipped with the standard equipment necessary for patient mobilization, particularly for bedbound and immobile patients, and nurses have been trained to use the equipment.

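### The adjusted LOF model includes EM adherence and lying time, which arise after EM starts; no fit is assigned to Aim 3, and this one would not give the total EM effect

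*Combined protocol and SAP*

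**What the plan says.** Aim 3 (III. Specific Aims) is "To determine the effectiveness of EM at improving the functional status of older adults during CICU admission", and also to improve longer-term outcomes. The primary outcome (VI. Methods, Outcome Measures) is LOF at CICU discharge, 1 month and 12 months. The same section states: "The results from the intervention cohort will be compared to the pre-intervention cohort for all results". It names no model for that comparison.

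Data Analysis specifies a cumulative logit model for the repeated LOF measurements, fitted by GEE, which "will then be adjusted using covariates of interest, such as age, sex, EM adherence, time spent lying in bed, and illness severity score". The list is open-ended, and the wording implies a first fit without these covariates. No cohort or cohort-by-time term is written, and neither fit is tied to an aim. Separate linear regressions are planned for predictors of change in LOF and predictors of EM adherence.

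The two covariates at issue come from these sources:

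- **EM adherence.** Under Intervention, "LOF, activity attempts/completion, and adverse safety events will be recorded on an EM flowsheet", and "Weekly audits will be performed by the nurse champion to assess for adherence to the EM protocol". In the pre-intervention period nurses record LOF "but will continue usual mobilization practices". Mobilization activities are nevertheless extracted for that cohort, and safety events are to be counted "over the total number of attempted mobility activities".
- **Lying time.** It comes from an accelerometer worn by consenting substudy participants from the CICU stay to hospital discharge, with five monitors in all (Intervention; Instruments). Section IV.D, item 6, presents lying time as something that could be changed. Aim 4 treats it as an exposure.

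Some pre-EM information is already planned. In the pre-intervention period "nurses will ascertain and record the prehospital LOF, admission LOF, and LOF on the day of CICU transfer", and the Clinical Frailty Scale (CFS) is scored on admission. The illness severity score named in Data Analysis is in neither extraction list (Pre-intervention; Data Collection Procedures).

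**The concern.** Aim 3 asks what introducing EM does to LOF. That total effect includes everything EM achieves by getting patients to do more and lie down less. A covariate that EM itself changes, or that exists only because EM is running, removes part of that effect from the cohort coefficient or makes the coefficient answer another question.

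This is a non-randomised pre/post study, so a reader will look to the adjusted fit for the effectiveness result. The only adjusted GEE described for LOF carries two such covariates. The implied unadjusted fit does not have this defect, but it leaves differences in case mix between the two periods uncontrolled. As written, neither fit is a satisfactory Aim 3 analysis, and the choice between them is open until the data are in.

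**Working it through.** The plan gives no effect size, adherence level or power calculation, so there is no figure of its own to reproduce. The check has four steps.

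**1. What the cohort term means once adherence is in the model.** Data Analysis gives no coding for the pre-intervention cohort. There are three possibilities:

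| Adherence before EM | Cohort term |
|---|---|
| Missing | A complete-case fit keeps 0 of about 75 pre-intervention patients; no contrast can be estimated |
| Coded 0 | EM effect at zero adherence |
| Built from activities in both cohorts | EM effect leaving out what runs through extra activity |

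None of these is the total effect.

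**2. Illustrative size for adherence.** From the plan: 75 and 300 patients (Availability of Participants) and three time points. Assumed: total odds ratio (OR) 2.0; adherence mean 67%, SD 20% under EM; where it is built in both cohorts, pre-EM mean 35%, SD 20%.

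If half the log OR runs through adherence, the remainder is about exp(0.5 × ln 2) = 1.41. The simulation used proportional odds, age, sex and severity in every model, within-patient correlation 0.6, GEE with robust SEs and 500 replicates. It gave these median results:

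| Model | OR if none / half / all of the effect runs through adherence | SE of log OR |
|---|---|---|
| Pre-EM covariates only | 2.0 (total effect) | 0.20 |
| Plus adherence, coded 0 before EM | 2.06 / 1.46 / 1.01 | 0.36 |
| Plus adherence, built in both cohorts | 2.05 / 1.45 / 1.02 | 0.24 |

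The SE ratios are 0.36/0.20 = 1.8 and 0.24/0.20 = 1.2. A closed form agrees, with p = 300/375 = 0.8:

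- Coded 0: √(1 + (1 − p)m²/s²) = √(1 + 0.2 × 0.67²/0.20²) = 1.80. It is 1.34 at mean 50%, SD 25%, and 2.59 at mean 80%, SD 15%.
- Both cohorts: √(1 + p(1 − p)d²/s²), with d = 0.67 − 0.35 = 0.32, = √(1 + 0.16 × 0.32²/0.20²) = 1.19.

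**3. Lying time as a mediator.** Assume EM lowers lying time by 2 h (SD 3 h). In the same kind of simulation the cohort OR without lying time is 1.99, 1.94 or 1.79 when none, half or all of the effect runs through it. (It falls below 2.0 because odds ratios are non-collapsible.) With lying time in the model it is 1.99, 1.41 or 0.98.

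**4. Lying time: coverage and timing.**

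- Coverage, at an assumed 9.5 days of wear (the mean hospital stay): 5 × 365/9.5 = 192 patients in 12 months, and 192/300 = 64%. If both cohorts wear monitors over 15 months, 5 × 456.25/9.5 = 240, and 240/375 = 64%. These are ceilings, with no idle monitor and no refusal. At 12 days of wear, 5 × 365/12 = 152 in 12 months. All 300 could be covered only at 5 × 365/300 = 6.1 days or less.
- Timing, on mean stays of 3.3 CICU days and 9.5 hospital days: (9.5 − 3.3)/9.5 = 65% of wear days fall after CICU discharge, the first primary time point.

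**The case against.** The strongest reply is that the plan never says the adjusted fit is the Aim 3 comparison. The list is open-ended, an earlier fit is implied, and the adjusted model may be meant for Aim 4 or for the search for predictors of responsiveness. This stands in part: the harm is conditional, and the plan does not exclude a total-effect estimate. It does not dispose of the point. Predictors of change in LOF already have their own linear regressions, the cohorts are to be compared on every result, and the adjusted GEE is the natural one to report in a non-randomised design.

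Several stronger readings are tempting, and the documents do not support them:

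- **That the GEE is the only LOF model.** Linear regressions for change in LOF are also planned.
- **That lying time would mostly follow the CICU-discharge outcome.** This holds only if it is averaged over the whole wear period. Outcome Measures lists total and daily average times, and no window is set for the covariate. The 65% also uses means over all admissions, including stays under 24 hours, which the study excludes.
- **That EM could be made to look harmful.** With severity in the model, and correlated about −0.5 with adherence, the simulated OR was 1.48 (half through adherence, coded 0). It fell below 1, to 0.65, only when severity was left out. Severity is a named covariate, and its absence from the extraction lists does not show that it will not be collected.
- **That both cohorts certainly wear monitors.** Enrolled participants are approached, but that paragraph sits under Intervention. If only EM patients wear them, lying time meets the same estimability problem as adherence.

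It is also fair that the attenuation follows directly from the assumed mediated share, and that a model with both covariates together was not evaluated.

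**Conclusion.** The concern holds as an unassigned analysis with conditional harm, and it should be fixed before analysis. Confidence is high that the named adjustment set contains two variables arising after EM starts, that no cohort term is written, and that no fit is assigned to Aim 3. Confidence is also high that the adjusted fit, if used for Aim 3, would not estimate the total EM effect wherever part of that effect runs through adherence or lying time.

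The realised size is unknown. The fall from 2.0 to about 1.45, with the SE 1.2 to 1.8 times as large, rests on the assumed OR, adherence distribution and half-mediated share. Other adherence levels under zero coding give SE ratios from 1.34 to 2.59. The 64% coverage ceiling rests on an assumed 9.5 days of wear.

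**What to change.** In Data Analysis, name one model as the Aim 3 estimate: the cumulative logit GEE with cohort, time and cohort-by-time, adjusted only for variables fixed before EM. A suitable set is age, sex, prehospital LOF, admission LOF, CFS score and admission illness severity. Other pre-EM sets would also be valid, provided the choice is made in advance. Add the severity score to the extraction list and name the score. Report the unadjusted fit as supportive.

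Take EM adherence and lying time out of the cohort comparison. Use adherence in an exploratory analysis within the intervention cohort. Use lying time in a separate Aim 4 model restricted to wear time before the outcome, which means CICU days when the outcome is LOF at CICU discharge. State which cohorts wear the monitors.

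The cost is SAP wording and one more extracted variable, with no extra patients or visits. The change does not remove secular trends between the two periods, so the estimate keeps the usual limits of a pre/post design.

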There are few available tools on how to implement an EM program, particularly in an acute cardiovascular unit. A lack of written protocols or guidelines, as well as insufficient clinician knowledge, has been identified as a barrier to implementing EM in critical care units.¹⁸

6. Patient positioning and activity in patients with acute cardiovascular disease: Precise identification of patient position (lying, sitting, and standing) and physical activity using body-worn sensors is now possible due to improvement in accelerometer technology. Accelerometry has been validated in numerous populations, including in the ICU, mainly in the context of mechanically ventilated patients.³⁰ However, previous studies in the ICU were limited by small sample sizes and short duration of patient monitoring, ranging from 60 minutes to 48 hours, and monitoring did not extend beyond ICU unit stay.³⁰ *There are also no studies in the literature specifically looking at positioning and activity in patients with acute CV disease.* It is important to understand the time spent in the different mobility positions and the relationship with functional outcomes in older adults with acute CV disease. Decreasing the duration of time spent in a lying position is a potentially modifiable factor.

V. PRELIMINARY STUDIES

During my Cardiac Intensive Care fellowship at Cedars-Sinai Medical Center in Los Angeles, CA, I participated in the EM program and instituted frailty screening in the CICU. We used a level of function (LOF) assessment tool in the EM program that ranged from 1 to 5, where 1 was bedbound and 5 was ability to walk > 50 feet (see sidebar). Preliminary analysis of the retrospective cohort of 264 patients with acute cardiovascular disease undergoing EM showed that 90 (34.1%) patients were frail, 65 (24.6%) were vulnerable, and 109 (41.3%) were not frail. We found a moderate correlation between prehospital LOF and frailty ($r = -0.580, P=0.01$). Prehospital LOF was higher in nonfrail elderly than in frail elderly (mean score of 3.71 ± 0.61 vs. 2.59 ± 1.03 ; $P < 0.001$). LOF improved in both nonfrail and frail elderly during CICU stay, however, there was greater improvement in LOF in the frail group (mean increase of 0.53 vs 0.70; $P < 0.01$). The initial data analysis suggests that frailty status is a potential predictor of responsiveness to EM. Further analysis of this dataset is needed to identify other predictors of responsiveness to EM in the CICU.

Progressive Mobility	

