A multidisciplinary EM implementation team developed a LOF assessment tool targeted for the CICU patient population. The assessment tool was created to be easy to use, quantitative, nurse-driven, and potentially generalizable to other CICUs. The creation of the EM team and EM program was an initiative of the Quality of Care Committee in the Division of Cardiology at the Jewish General Hospital.

All patients admitted to the CICU are eligible for the EM program, except for patients meeting pre-defined hemodynamic, respiratory, neurologic, or in-dwelling device criteria. The exclusion criteria were chosen based on expert guidelines for EM safety³¹ and adapted for the acute cardiovascular patient population through collaboration with the multidisciplinary EM team.

For entry into our study, the inclusion criterion is age ≥ 60 years and exclusion criteria are CICU stays less than 24 hours and patients with prehospital LOF 0 (immobile), LOF 1 (bedbound) or 2 (can sit in chair only). Cardiac surgery patients will also be excluded. Patients with a pacemaker or defibrillator will not be included in the bioimpedance substudy (contraindication for use of bioimpedance scale). For the pre-intervention cohort, patients will be prospectively enrolled over a 3-month period by a member of the research team during CICU admission. Following the 3-month pre-intervention period, the intervention (EM program) will be implemented and patients will be prospectively enrolled during CICU admission over a 12-month period by a member of the research team. Informed consent will be obtained for all participants during enrolment by a member of the research team.

Pre-intervention

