housed in the Frailty Assessment Unit of the JGH's cardiovascular ward and can be used at the point of care. The BIA scales provide a full analysis of body composition in less than 1 minute, including determination of skeletal muscle mass. There are no risks associated with the bioimpedance scale, except for patients with a permanent pacemaker or defibrillator, who will be excluded from this trial (the reason being that bioimpedance scale currents may disrupt the functioning of pacemakers or defibrillators).

Post-discharge follow-up

One month and 12-months post-discharge a member of the research team will call participants by phone to assess for health-related quality of life and functional status. The member of the research team will determine the current LOF and administer the Short-Form 36-Item Health Survey (SF-36) and Barthel index.

Outcome Measures

The primary outcome will be the LOF at CICU discharge and at 1 and 12 months post-hospitalization. Secondary outcomes are (1) Short Form (SF)-36 physical component summary score at 1 and 12 months, (2) SF-36 mental component summary score at 1 and 12 months, (3) Barthel index score at 1 and 12 months, (4) length of hospital stay, and (5) discharge to healthcare facility (including rehabilitation facility, convalescence, transfer to another acute care facility, and long-term care placement).

The SF-36 is a patient-reported survey of health and is the most widely used health-related quality of life instrument.⁵³ The physical and mental component scores are subsets of the SF-36 with score ranges from 0-100 and are calibrated for an average score of 50, using Canadian normative data, with higher scores indicating less disability.⁵⁴ The Barthel index is a disability measure validated in elderly cardiac patients that incorporates ten activities of daily living (i.e., feeding, dressing, incontinence).^{55, 56} Only two components of the Barthel index address mobility issues (transfer and mobility), so there is minimal direct overlap with the LOF scale score. The score range is 0–20, with lower scores indicating increased disability.

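### The model that names lying time (Aim 4) does not name starting LOF or frailty, so its lying-time coefficient is confounded; name them, and cut the exposure window at the outcome

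*Combined protocol and SAP*

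**What the plan says.** Aim 4 (III. Specific Aims) is "To evaluate the association of daily time spent lying in bed with functional status at CICU discharge and following hospital discharge". Hypothesis 2 is likewise worded as an association, with quality of life and function at longer-term follow-up. Item 6 of the knowledge gaps (IV. Background, D) adds: "Decreasing the duration of time spent in a lying position is a potentially modifiable factor".

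Under Outcome Measures, "The primary outcome will be the LOF at CICU discharge and at 1 and 12 months post-hospitalization". Under Data Analysis, "a cumulative logit model for repeated measurements will be fitted using generalized estimating equations", to be "adjusted using covariates of interest, such as age, sex, EM adherence, time spent lying in bed, and illness severity score". No other analysis text names lying time. The same section adds: "Predictors of change in LOF during CICU stay and following hospitalization will be assessed using linear regression", without listing the predictors.

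Starting status is collected. Before the intervention, "nurses will ascertain and record the prehospital LOF, admission LOF, and LOF on the day of CICU transfer". In the intervention period LOF goes on the EM flowsheet. CFS is assessed on admission, and Data Collection Procedures lists both LOF assessments and CFS. No section says that any of these enters a model with lying time.

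Monitors are worn from the CICU stay to the end of the hospital stay (VI. Methods, Intervention).

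**The concern.** The low end of the LOF scale is described by confinement to bed or chair. The exclusion criteria show this: "patients with prehospital LOF 0 (immobile), LOF 1 (bedbound) or 2 (can sit in chair only". Those exclusions apply to prehospital LOF only. In the pilot, eligible patients had a mean admission LOF of 2.3 (SD 1.2), so many would start near the bed-or-chair range. Nurses also match activities to current LOF. Starting LOF therefore influences lying time, and it plausibly influences later LOF too. A model without it gives part of that influence to lying time.

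What is at stake is the meaning of a positive Aim 4 result. As listed, the model cannot separate an effect of lying on function from an effect of poor function on lying, while the Background invites the first reading. The point concerns the lying-time coefficient only, not the EM effect.

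**Working it through.** **Plan's own figure.** There is none to reproduce: the documents give no alpha, power, effect size or sample size for Aim 4. A two-sided 5% level is assumed throughout.

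**Inputs from the documents.** Admission LOF has mean 2.3 and SD 1.2 (V. Preliminary Studies). Five monitors are available (Instruments). Mean hospital stay is 9.5 days and mean CICU stay 3.3 days (Availability of Participants). Monitor ceiling over 12 months: 5 × 365 / 9.5 = 192 patients, if every monitor is in use every day.

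**Assumed inputs.** Two standardised direct links: admission LOF to lying time (fewer hours at higher LOF), and admission LOF to later LOF. Illness severity correlates 0.3 with worse LOF (0.6 in one variant) and has its own link of 0.2 to both lying time and later LOF.

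**Simulation.** Cumulative logit model, three timepoints, independence working correlation, patient-clustered sandwich standard errors, 600 runs per cell. Covariates were lying time, severity, age, sex, adherence and timepoint. The true effect of lying time is zero. Share of runs with P<0.05 for lying time, without starting LOF:

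| Links (LOF-lying / LOF-later LOF) | n=50 | n=100 | n=192 |
|---|---|---|---|
| 0 / 0.5 (check) | 8% | 6% | 5% |
| 0.2 / 0.3 | 11% | 9% | 14% |
| 0.3 / 0.5 | 22% | 38% | 60% |
| 0.5 / 0.5 | 50% | 79% | 98% |
| 0.5 / 0.5, severity-LOF correlation 0.6 | 34% | 57% | 83% |

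Where the links are moderate, nearly all rejections point to more lying, worse LOF. The first row shows that the excess comes through starting LOF.

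**Hand check.** For one timepoint, the induced correlation is about the product of the links. With z = atanh(r) × √(n − 3), the rejection rate is Φ(z − 1.96) + Φ(−z − 1.96).
- 0.2 × 0.3 = 0.06: z = 0.59 at n=100, giving 9%; z = 0.83 at n=192, giving 13%.
- 0.5 × 0.5 = 0.25: z = 2.52 at n=100, giving 71%; z = 3.51 at n=192, giving 94%.

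The simulated 79% and 98% are somewhat higher; three timepoints carry more information than one.

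**Change-in-LOF regression, if lying time is entered.** Subtracting admission LOF does not remove the problem. With equal SDs and links of 0.5, later LOF rises 0.5 per unit of admission LOF, so change moves by 0.5 − 1 = −0.5. The induced association with lying time is (−0.5) × (−0.5) = +0.25, against (−0.5) × 0.5 = −0.25 for the level of LOF. The sign reverses: more lying, more gain. Simulated rejection at 0.5/0.5 is 50%, 79% and 97% at n=50, 100 and 192. The earlier cohort in Preliminary Studies fits this direction: the frail group had lower prehospital LOF (2.59 against 3.71) and gained more (0.70 against 0.53).

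**What adjustment achieves.** With admission LOF added, the LOF model rejects in 5-7% of runs at n=100-192 and in 6-9% at n=50. That holds only because lying time was generated from admission LOF, not from LOF later in the stay. In a simpler linear model for discharge LOF, lying time was made to follow the mean of admission and discharge LOF, again with no effect of lying. LOF explained 10-25% of the variance in lying time, and the admission-discharge correlation was 0.6-0.75. With categorical admission LOF in that model, the test still rejects in about 22-76% of runs at n=100 and 39-97% at n=190.

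**Exposure window.** If the CICU stay comes first, on average 9.5 − 3.3 = 6.2 of 9.5 days of wear fall after LOF at CICU discharge has been recorded. A daily average over the whole wear period would let exposure follow outcome.

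**The case against.** Aim 4 and Hypothesis 2 claim only association. If low LOF makes patients lie more, a non-zero coefficient is a real association, and no analysis text claims an effect. This stands. The difficulty lies in the causal reading that the hedged Background sentence invites.

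The covariate list is open, so starting LOF could still be added. This also stands: it is an omission from a list, not a decision to leave LOF out. But the choice of the main confounder would then be open after the data are seen.

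The correlations are assumed. This stands too, and with weak links the excess over 5% is small. Pilot prehospital LOF averaged 4.7 (SD 0.6), near the top of the 0-5 scale. Recovery toward that level could compress LOF at 12 months and weaken its link to admission LOF.

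A reader might infer that Aim 4 is bound to be positive, or that Hypothesis 2 would be confirmed whatever the truth. The documents do not support either. The rate runs from about 9% to 98% at n=100-192 across the links shown, nothing was computed for SF-36 or Barthel, and the two LOF analyses are biased in opposite directions. A reader might also infer that adding admission LOF restores the nominal error rate. It does not if lying time tracks LOF through the stay.

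**Conclusion.** The concern holds as a confounding problem that the plan can reduce with baseline data it already collects. As listed, the lying-time coefficient mixes any effect of lying with the effect of starting function. At n=100-192 with no true effect, the rejection rate is about 9-14% for weak links and 79-98% for moderate ones, or 57-83% for moderate links when severity is a strong proxy for LOF. These figures rest on assumed correlations, a 5% level and, at the upper size, full use of all five monitors. The scale definitions make a moderate link plausible for lying time and LOF at CICU discharge; for 12 months the documents give less support. Adjustment reduces the bias without removing it, so even the adjusted result would not by itself show that lying time is a modifiable cause.

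**What to change.** In Data Analysis, give Aim 4 its own paragraph:

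- Every model that contains lying time, including the change-in-LOF regression, includes admission LOF (categorical), prehospital LOF and CFS, together with age, sex, EM adherence and illness severity.
- For LOF at CICU discharge, only lying time recorded before that assessment counts as exposure.
- The result is reported as an adjusted association. The coefficient without the starting-status terms is labelled descriptive.
- The text states that confounding remains because LOF changes during the stay, so the result does not by itself show lying time to be a modifiable cause.

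Cost: analysis wording. LOF and CFS are already recorded. The illness severity score is a named covariate but does not appear in the data-collection lists, so its capture should be confirmed. The downside is up to five indicator terms for the six admission LOF levels, plus prehospital LOF and CFS, and a wider interval. If starting status explains a quarter of the variance in lying time (0.5² = 0.25), the standard error grows by roughly 1/√0.75 = 1.15, before any gain from explaining the outcome.
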